### 3. Rationale

Bangladesh is a highly endemic area for diarrhoeal diseases and persistent diarrhoea is becoming more recognised as a serious problem. The clinical management of persistent diarrhoea is not easy, and is based mainly upon dietary intervention and manipulation. This clinical condition is associated with marked malabsorption of nutrients, particularly fat. The underlying pathomechanism is not yet clearly understood. Observations in ICDDR,B hospital indicates that substitution of dietary LCTs by MCTs helps in clinical recovery of patients suffering from persistent diarrhoea. If found effective, it may be usefully applied in the dietary management. In addition, the study may provide useful information on the pathomechanism of nutrient malabsorption, so that other therapeutic interventions could be considered. This study will help to make a more rational approach in

formulating an appropriate dietary and clinical management scheme which will reduce malabsorption of nutrients and the associated risks in persistent diarrhoea in children.

#### **B. SPECIFIC AIMS**

1. To estimate and compare fat, carbohydrate and protein absorption during persistent diarrhoea from the defined diets.
2. To assess and compare the impact of the specific diets on the clinical course of the disease.
3. To determine intestinal and pancreatic functions during the diarrhoeal state, and correlate them with nutrient absorptive capacity during the same state.

#### **C. METHODS OF PROCEDURE**

##### **Selection criteria :**

Age : 3-12 months

Sex : Only male children

Duration of diarrhoea: > 2 weeks but < 6 weeks

Diarrhoea with acute onset

##### **Exclusion criteria**

1. Stool volume of less than 40 g/kg body wt. during the first 24 hours of admission (baseline observation period).
2. Presence of complications such as high fever (  $>38^{\circ}\text{C}$  ), severe infections, electrolyte imbalance, altered level of consciousness, and presence of organisms such as cholera or shigella in stool requiring antibiotics.
3. Clinically apparent severe degree of marasmus (wt for age  $<55\%$  of NCHS

median wt) or Kwashiorkor.

4. Patients who have received antibiotics within the previous 72 hours.

Informed consent will be obtained from the parents/legal guardian before inclusion into the study.

Detailed clinical history will be obtained and a thorough physical examination will be performed including anthropometric measurements (recumbent length, body weight, mid-arm circumference and triceps skinfold thickness). Vital signs will be recorded every 8 hours. Round the clock routine clinical care will be provided, and regular assessment of patients condition will be monitored and recorded.

#### General management

All hydration including initial hydration will be made by I.V. solutions during the entire study period. During the first 24 hours (baseline observation period), baseline data on stool output, vomitus, food intake, and requirement of I.V. fluids will be obtained, and stool output rate will be calculated. The diet during this period will be half strength milk formula. Breastfeeding will be continued and its intake will be measured.

The eligible patients will be randomly assigned to one of the two dietary groups. In the next 24 h, the patient will receive the study diet (pre-balance period). The oral intake will be restricted upto 200 ml/kg.d. All feed will be given hourly.

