INTERNATIONAL CENTRE FOR DIARRHOEAL DISEASE RESEARCH, BANGLADESH  
[name]

TO : Chairman, Research Review Committee  
 FROM : [name], Reviewer *[name]* DATE: 6/9/88  
 SUBJECT : Review of protocol no. 88-021 entitled "Trial of coconut oil based comminuted chicken meat diet in persistent diarrhoea in children - metabolic balance study" - [name]

Description:

The investigators planned to study 50 male children (3-12 months age group) 25 in each group to compare the impact of a modified chicken-based diet containing either coconut oil or soyabean oil, on nutrient absorption and clinical course in persistent diarrhoea. They also planned to do metabolic balance study for the underlying functional derangements associated with malabsorption in persistent diarrhoea. The intestinal and pancreatic functions will also be evaluated during diarrhoeal state and at convalescent state for correlation with nutrient absorptive capacity. Patient will be studied for 8 days including 72 hours balance study period. Various tests like intestinal permeability tests, breadth hydrogen test, urinary BT-PABA excretion test, Duodenal intubation fluid for microscopy and culture, intensive metabolic balance study etc. will be performed during the study period.

Adequate of background information:

The investigators discussed various factors associated with persistent diarrhoea, with special emphasis on fat malabsorption. As high as 92% of children with prolonged diarrhoea could be associated with fat malabsorption. Studies have shown that digestion, absorption and transport of fats are dependent upon the type of fatty acids attached to glycerol in the triglyceride molecule. Medium chain triglycerides have been found to be superior than usual dietary fat of Long chain triglycerides.

Critique of the Research plan:

The aims of the protocol is well defined, approach to the problem is valid. The experimental design is adequate, the number subjects to be studied statistically calculated. However, I have the following few comments:

1. In fact, the protocol clearly has two distinct components:  
(a) Metabolic balance study in persistent diarrhoea  
(b) Comparative clinical outcome study

2. This is not a blind study. Perhaps, it is possible to make blind. It is not clear what appropriate measures will be taken by the investigators to exclude biasness.

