## 10. Abstract summary:

Persistent diarrhoea is increasingly being recognised as a difficult clinical situation both from pathophysiological and management point of views. Malabsorption of nutrients causing severe nutritional deficit seen in persistent diarrhoea is mostly related to functional derangements of the gastrointestinal tract. The most important aspect of clinical management in persistent diarrhoea is dietary manipulation. In a metabolic balance study, a diet based on coconut oil which is a rich source of medium chain triglycerides, will be compared with an isocaloric similar diet based upon soyabean oil. Fifty children aged 3-12 months and suffering from diarrhoea for more than 2 weeks will be randomly assigned into the two dietary groups. Clinical response and coefficients of nutrient absorption will be recorded, related to the functional derangements as identified by various laboratory investigations, and then compared between the two dietary groups. Subjects will be followed up for 2 months to monitor prognosis and also to ensure appropriate dietary management at home. Data generated is expected to be

useful towards identification of more appropriate and alternative diets as well as to provide insights into the pathomechanism.

11. Reviews :

Research Review Committee \_\_\_\_\_

Ethical Review Committee \_\_\_\_\_

Director \_\_\_\_\_

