**Use of antibiotics :** Patients from whom cholera, shigella or salmonella are isolated on admission (stool culture reports will be available by 48 hours, i.e. before balance period starts) will be transferred from the study and treated with appropriate antibiotics. Patients having *E. histolytica* (haematogenous form) will not be included in the study and will be treated accordingly. Patients from whom *G. lamblia* or *E. histolytica* (cyst form) is isolated, or who have small intestinal bacterial overgrowth as found after culture of jejunal aspirate, will be treated with specific antimicrobials after the study period is finished. Only penicillin, which has got minimal effect upon enteric pathogens, may be used for mild infections during the study period.

**Management of patients who failed on study diets :** Antibiotics, if indicated as described above, will be given. Management of those patients who fail to respond will be tried by more dietary manipulation through elimination of different dietary components and maintaining parenteral hydration and nutrient support.

**Transfer from study :** Any child developing sepsis, convulsion, enterocolitis, pneumonia, or any other serious condition will be immediately transferred to the intensive care unit, and will be excluded from the study. Data upto the point of transfer or deviated course for intervention will be considered in analysis.

**Follow up :** To monitor the patients' prognosis and also to ensure proper dietary management, a weekly follow-up for first 2 weeks and then bi-weekly for another 6 weeks will be made. The patients' parents will be asked to come to the hospital for the follow-up check-ups. 6 weeks after discharge, trial with cow's milk test feed will be given during follow-up

visit and the patient observed for 6 hours. A repeat breath H2 test will be performed at the same time. If tolerated, then transition to normal milk-based home will be advised, otherwise milk-free diet will be continued.

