**Definations :**

1. Diarrhoea - passage of 4 or more liquid motions within 24 hours.
2. Persistent diarrhoea - diarrhoea persisting for more than 2 weeks following an episode of acute diarrhoea.
3. Cessation of diarrhoea - passage of soft stool or formed stool, and no liquid stool in 48 hours.
4. Dietary failure - patients in whom diarrhoea does not stop by 7 days after starting study diet.

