### Response Variables

1. Coefficient of absorption of fat, protein and carbohydrate.
2. Stool output (g/kg/24 hrs) over the study period
3. Duration of diarrhoea.
4. Weight gain (or loss) by day 7
5. Amount of I.V. needed (a proxy indicator of diarrhoeal severity)
6. Improvement in intestinal function as measured by intestinal mucosal permeability test
7. Proportion of success in each dietary group
8. Growth rate and morbidity during follow up

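### No masking is described although the diets differ only in the oil, which leaves duration, dietary success, I.V. amount and transfers open to observer bias

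*Protocol*

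**What the plan says.** Under General management the protocol assigns eligible children at random: "The eligible patients will be randomly assigned to one of the two dietary groups". From there to the list of response variables, the methods mention no coded feeds, no masked assessor and no masking of ward staff, parents or laboratory.

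The composition table under Balance study gives both diets the same chicken, glucose, salts, energy (50 kcal/100 ml) and osmolality (220). Only the oil differs: 35.0 g/l coconut in Diet A, 35.2 g/l soyabean in Diet B.

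The review memorandum dated 6/9/88, bound in the same file, says "This is not a blind study. Perhaps, it is possible to make blind" and continues: "It is not clear what appropriate measures will be taken by the investigators to exclude biasness".

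Cessation of diarrhoea is defined as "passage of soft stool or formed stool, and no liquid stool in 48 hours", and dietary failure as "patients in whom diarrhoea does not stop by 7 days after starting study diet". Response Variables lists duration of diarrhoea, proportion of success and the I.V. amount. The paragraph on transfer from the study ends with a catch-all for other serious conditions and adds: "Data upto the point of transfer or deviated course for intervention will be considered in analysis".

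The expected direction is on record. The Background reports an informal trial at the centre in which coconut oil went with more than a 20% shorter duration, and the Rationale says hospital observations favour MCT substitution.

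**The concern.** Cessation turns on whether someone on the ward calls a stool soft or liquid. That reading fixes the duration of diarrhoea, the only endpoint used to size the trial, and also decides dietary failure at 7 days and hence the proportion of success. I.V. amount is counted as a response, but staff set it. Transfer is likewise a staff decision, and it ends the child's contribution to the analysis. If the people making these calls know the diet and expect coconut oil to do better, a small systematic lean could be read as a treatment effect. Two feeds this alike look like good candidates for masking. The gap also has to be closed before the first feed is given: no later analysis plan can mask a ward in retrospect.

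**Working it through.** **Inputs from Calculation of sample size:** mean duration 3.75 days (coconut) and 4.91 days (soya), SD 1.31 days, two-sided 5% level, 80% power, difference entered as 1.15 days, 22 per group, 50 enrolled in all.

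**The plan's own figure.** 2 × 1.31² × 7.9 / 1.15² = 20.50; × 29/27 = 22.02. This agrees with the stated 22 per group. With the exact difference 4.91 − 3.75 = 1.16 the result is 21.64, which also rounds up to 22. Masking would not change this number.

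**What a lean would do.** The protocol gives no size for observer bias, so the lean *b* (days, in favour of coconut oil) is an assumption, shown as a range from small upwards. The true difference is set to zero.

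- Standard error at 22 per arm: 1.31 × √(2/22) = 0.395 day.
- Critical t on 42 df: 2.018, so the smallest observed difference that reaches significance is 2.018 × 0.395 = 0.80 day.
- Non-centrality = *b* / 0.395. The false-positive rate is the chance that a non-central t on 42 df falls outside ±2.018.
- At 25 per arm (all 50 analysed, split equally): standard error 0.371, 48 df, critical t 2.011, smallest significant difference 0.74 day.

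| Assumed lean *b* (days) | *b* / 1.16 | Two-sided false-positive rate, 22 per arm | 25 per arm |
|---|---|---|---|
| 0 | 0% | 5.0% | 5.0% |
| 0.1 | 9% | 5.7% | 5.8% |
| 0.2 | 17% | 7.9% | 8.3% |
| 0.3 | 26% | 11.5% | 12.5% |
| 0.5 | 43% | 23.6% | 26.2% |

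Almost all of the excess falls on the coconut side. At 0.5 day and 22 per arm, 23.5 of the 23.6 percentage points are results favouring coconut oil, against a nominal 2.5.

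**Which response variables are exposed.**

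- *Exposed:* duration of diarrhoea and proportion of success (both through the stool reading), I.V. amount, and the timing of transfer.
- *Much less exposed:* absorption coefficients (laboratory fat, nitrogen and calorimetry on a 72 h collection between charcoal markers), stool output in g/kg/24 h, weight change, and the assayed lactulose/mannitol ratio.

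**The case against.** Four points can fairly be made in the protocol's defence.

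- **The methods never call the trial open.** A reader might infer that staff certainly know the diet. The methods are silent; the only explicit statement is the memorandum's, and its author still recommended approval. What stands is that no masking is described and the protocol text does not answer the memorandum.
- **The leading outcomes are measured.** A reader might infer that the whole trial rests on subjective endpoints. The documents do not support that: nutrient absorption comes first in the major objective, in the Specific Aims and among the response variables, and it is a laboratory result. This objection stands and limits the point to the exposed variables above.
- **The lean is hypothetical.** A reader might take it to rival the planned effect, but the assumed values are 9% to 43% of 1.16 days and at the low end they hardly matter. The 48-hour rule cuts both ways: one lenient reading need not move the cessation date, while one borderline stool called liquid can restart the window. Nor do the documents show that ward staff were told of the informal trial, although the centre's own expectation is written down.
- **Masking may be imperfect.** The documents do not discuss the taste, smell or appearance of the oils. If coconut oil can be smelt, masking is weakest on the ward, where the risk arises. That limits the gain but does not remove the case for trying.

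**Conclusion.** The point holds in a limited form. The protocol describes no masking, its own file flags the gap, and the diets are close enough for coding to be a reasonable step. Duration, success or failure, I.V. amount and transfers are vulnerable in the direction the protocol expects; the measured outcomes are much less so. Under an assumed lean of 0.1 to 0.5 day, no true effect, SD 1.31 and 22 per arm, the false-positive rate for duration runs from 5.7% to 23.6% instead of 5%. These figures show how sensitive the comparison is. They are not evidence that bias will occur, nor do they estimate its size. The sample size is unaffected. This is a worthwhile, inexpensive improvement and not a flaw that invalidates the trial.

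**What to change.** Add to General management:

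- The diet kitchen prepares both feeds in identical containers labelled by study number, using several codes and not just A and B. The code list is held off the ward.
- Existing staff who record stool consistency, decide on I.V. volume and transfers, or run the assays work from the codes.
- The code is broken only for clinical need.

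In the report, present duration and success next to the measured stool weight and absorption results, and state how far masking held.

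**Cost:** the labelling work and keeping a code list. The number of children does not change. The smell of coconut oil may reveal some feeds, so ward masking may be only partial; the laboratory should be easier to mask.

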#### Balance study

The study diet will be continued, as started on 2nd day. The amount of diet provided to each patient will be 200 ml/kg/24 hour. At the 48th hour of admission, the first marker as charcoal tablet will be given. A 2nd charcoal marker will be given after 72 h at the same time of first marker. Time of appearance of first marker in stool will be taken as 0 h.

Collection of stool and urine will be started with the appearance of the first marker until 2nd marker comes out. 5 ml of acetic acid will be given in the collecting buckets. 72 h dietary intake will be measured and recorded. All vomitus will be collected in the same way. These samples will be kept at -20°C. Aliquotes of stool samples from homogenized 72 h collection will be taken and analysed for fat, nitrogen, and carbohydrates by subtracting those from total energy. Total energy content will be determined by calorimetry. Dietary and breast milk contents for fat, CHO and N will also be analysed. Total urinary N2 excretion/daily will be determined.

$$\text{Absorption coefficient} = \frac{\text{Intake} - \text{loss}}{\text{intake}} \times 100$$

Composition of diets/l

	Diet A	Diet B
Ground chicken meat	150.0 g	150.0 g
Glucose	20.0 g	20.0 g
Coconut oil	35.0 g	-
Soyabean oil	-	35.2 g
NaCl	1.0 g	1.0 g
Calcium lactate	0.5 g	0.5 g
MgCl 2	0.2 g	0.2 g
H 2 O upto	1.0 l	1.0 l
Energy kcal/100 ml	50	50
Osmolality	220	220

As elemental diets have been shown to cause micro-nutrient deficiency in patients suffering from prolonged sickness, a commercially prepared metabolite mixture containing multivitamins and essential minerals will be given to all patients daily for two weeks.

A disadvantage of using MCTs for longtime is the risk of developing

essential fatty acid (EFA) deficiency. To reduce this risk, safflower oil, a rich source of EFAs, will be applied topically during the period the patients are on study diets.

After recovery from diarrhoea, a transitional diet (half strength rice suzi) will be tried, and if tolerated, the patients will be sent home on this diet.

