**STATISTICAL CALCULATION**

**Calculation of sample size**

Expecting the mean duration of diarrhoea with coconut oil based formula to be 3.75 days and that of soya oil based formula to be 4.91 days, the sample size is calculated based upon the formula.

$$\frac{2\sigma^2(Z_{\alpha/2} + Z_{\beta})^2}{\delta^2} \times (f+3)/(f+1)$$

Where  $\sigma^2$  = pooled variance

$\delta$  = difference between the means

and  $f$  = degrees of freedom

With the confidence limit of 95% and power of 80%,  $(Z_{\alpha/2} + Z_{\beta})^2 = 7.9$ .

Substituting the values, the calculated sample size is

$$\frac{2 \times 1.31^2 \times 7.9}{1.15^2} \times \frac{29}{27} = 22$$

or 44 patients for both groups.

With anticipation of refusals and dropouts, a total of 50 patients will be enrolled into the study.

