### Data analysis

All data generated from the study will be entered into a microcomputer and appropriate statistical tests will be performed. The two study groups will be compared on admission and pre-randomisation data to assess their comparability. The response variables will be compared after evaluating the distribution so that appropriate tests could be applied. Chi-squared test, Student's 't' test, Mann-Whitney's 'U' test, Wilcoxon's Rank/Sum test and multiple regression analysis (keeping co-efficients of absorption of nutrients as the dependent variable) will be considered.

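### Breastfeeding status is known before assignment and milk fat enters the fat-absorption coefficient, but the plan neither balances nor firmly adjusts for it: an optional, low-cost gain in precision

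*Protocol*

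**What the plan says.** - **Allocation.** Protocol, General management: "The eligible patients will be randomly assigned to one of the two dietary groups". No strata, blocks or balancing factor are named.
- **Breastfeeding before assignment.** The same section says of the first 24 hours: "Breastfeeding will be continued and its intake will be measured". One exclusion criterion is "Stool volume of less than 40 g/kg body wt. during the first 24 hours of admission (baseline observation period". Eligibility therefore cannot be settled until that period ends, and assignment comes after it.
- **Breast milk in the balance.** Balance study: "Dietary and breast milk contents for fat, CHO and N will also be analysed". The intake and output sheet has separate breast-milk columns, fat among them. On the stool side: "Aliquotes of stool samples from homogenized 72 h collection will be taken and analysed for fat".
- **Diet volume.** Balance study: "The amount of diet provided to each patient will be 200 ml/kg/24 hour".
- **Size.** Calculation of sample size: "a total of 50 patients will be enrolled into the study".
- **Analysis.** Data analysis: "The two study groups will be compared on admission and pre-randomisation data to assess their comparability". The section then lists t, rank and chi-squared tests, and multiple regression with the absorption coefficients as outcome, as methods to be considered.
- **Endpoint.** The absorption coefficient for fat stands in the first item under Response Variables.

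**The concern.** In a breastfed child the fat coefficient mixes two sources, study oil and milk fat. Stool fat comes from one pooled collection, so the unabsorbed part cannot be traced to either source. If breastfed and other children differ in fat absorption, an analysis that ignores status carries that difference as extra between-child variance. With about 25 children per arm, chance can also give the arms unequal breastfed shares. The comparability check would reveal such an imbalance but does nothing about it. What is at stake is the precision of the fat comparison, in a small trial where the remedy uses a value already collected.

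**Working it through.** **The plan's own figure.** The sample size is for duration of diarrhoea: 2 × 1.31² × 7.9 / 1.15² = 20.50, and 20.50 × 29/27 = 22.02, which agrees with the stated 22 per group. Fat absorption plays no part in it, so nothing below changes it.

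**Inputs from the protocol.** 50 children enrolled (25 per arm), 44 required (22 per arm); oil 35 g/l; diet 200 ml/kg/d; diet energy 50 kcal/100 ml; glucose 20 g/l.

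**Assumed inputs.** Breastfed share p; milk volume b; milk fat 3.5-4.0 g/100 ml; energy factors 9 and 4 kcal/g; D, the difference in fat absorption between breastfed and other children. The protocol gives none of these.

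**1. Milk as a share of fat intake.**
- Oil: 0.035 g/ml × 200 ml/kg/d = 7.0 g/kg/d.
- Chicken fat, upper bound: (500 − 35 × 9 − 20 × 4)/9 = 11.7 g/l, so 0 to 2.33 g/kg/d.
- Share = milk fat / (7.0 + chicken fat + milk fat).

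| b (ml/kg/d) | Lowest | Highest |
|---|---|---|
| 25 | 0.875/10.21 = 9% | 1.0/8.0 = 12% |
| 50 | 1.75/11.08 = 16% | 2.0/9.0 = 22% |
| 100 | 3.5/12.83 = 27% | 4.0/11.0 = 36% |

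**2. Chance imbalance without stratification.** Breastfed counts in the two arms are taken as independent Binomial(n, p). The chance that they differ by 5 or more is:

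| p | 25 per arm | 22 per arm |
|---|---|---|
| 0.3 or 0.7 | 0.164 | 0.137 |
| 0.4 or 0.6 | 0.193 | 0.165 |
| 0.5 | 0.203 | 0.174 |

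At 25 per arm it falls to 0.110 for p = 0.2 or 0.8, and to 0.034 for p = 0.1 or 0.9. A 5-child gap at 25 per arm moves the unadjusted arm difference by 5/25 × D = 0.20 × D.

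**3. Variance from ignoring status.** V = 1 + p(1 − p)(D/SD)², with SD taken within breastfeeding groups. Equivalent number = 50/V. Power is Φ(2.80/√V − 1.96), for a contrast that the adjusted analysis would detect with 80% power.

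| D | V (p = 0.3 or 0.7; p = 0.5) | Equivalent of 50 | Power |
|---|---|---|---|
| 0.25 SD | 1.013; 1.016 | 49.4; 49.2 | 79% |
| 0.5 SD | 1.053; 1.063 | 47.5; 47.1 | 78% |
| 1 SD | 1.21; 1.25 | 41.3; 40.0 | 72%; 71% |

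**4. Which remedy recovers this.** Step 3 compares adjusted with unadjusted analysis, so the gain belongs to adjustment. Once the analysis adjusts, stratified allocation adds roughly 1/(44 − 3) = 1/41, about 2%.

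**5. How large D can be through milk share alone.** By that route D is about the milk share × the gap between milk-fat and diet-fat absorption.
- At b = 50, D = 5 points needs a gap of 5/0.222 to 5/0.158, or 23-32 points; D = 15 needs 68-95 points.
- At b = 25, D = 15 needs at least 15/0.125 = 120 points, which is impossible.
- At the top share, 36% at b = 100, D = 15 still needs about 41 points.

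The protocol gives no SD for fat absorption, so these points cannot be converted into SD units.

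**6. What stratified blocks guarantee.** With blocks of 4 and 6, the largest gap in the breastfed list is half the largest block, 3 children (0.12 × D at 25 per arm). That holds at assignment only. Under Use of antibiotics, children with a positive culture for cholera, shigella or salmonella leave once results arrive by 48 hours, after assignment and before the balance period. Transfer from study removes others later.

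**The case against.** The strongest reply is that the protocol makes no error here. It states random assignment without fixing the method, and covariates are commonly left to an analysis plan. Regression on the absorption coefficients is already foreseen and the breast-milk data are collected. The allocation gap by itself is worth about 2%. The choice of breastfeeding is also open to argument: the Background stresses mucosal damage, bile salts, bacterial overgrowth and pancreatic function, and baseline stool output is known at assignment too.

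Most of this stands. The absent covariate list is not a fault, and the point is an improvement to the design. Two things remain in its favour. A later analysis plan can add adjustment but cannot restore balance at assignment. And breast milk has a direct claim among possible factors, because it enters both the intake and the loss from which the coefficient is computed.

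A reader might infer more than the documents support:
- **That the fat comparison is biased.** Chance imbalance under randomisation is not bias, and the test's error rate allows for it.
- **That the trial is underpowered.** The sample size rests on duration of diarrhoea and reproduces.
- **That stratification would save 9-10 of 50 children.** That figure needs D = 1 SD and comes from adjustment.
- **That the weaker oil contrast in breastfed children is the fault.** This dilution follows from continuing breastfeeding, and neither remedy removes it.

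**Conclusion.** The point holds as an optional, low-cost improvement. The protocol has a baseline value tied directly to its first-listed response variable, available before assignment, and makes no firm use of it in allocation or analysis. With 30-70% of children breastfed, the variance cost of ignoring it is 1-2% if D is 0.25 SD (less than one child of 50) and 5-6% if D is 0.5 SD (about 3 children). It is 21-25% only if D is 1 SD, which would probably need some difference between the groups beyond milk share; the protocol documents none. The chance of a gap of 5 or more breastfed children is 16-20% at 25 per arm and 14-17% at 22 per arm, and smaller if nearly all or very few children are breastfed. Breastfed share, milk intake and D are all assumptions.

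**What to change.** 1. **Data analysis (nearly all the gain).** State that the fat-absorption comparison will be adjusted for, or stratified by, breastfeeding status, yes or no, from the baseline 24 hours. Do not use milk intake during the balance period, because the study diet could change it.
2. **General management (about 2% more).** Stratify the allocation on the same status, with concealed lists and varied small blocks, for example 4 and 6, in each stratum.

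The cost is one extra allocation list and one sentence in each section; no new data are needed. Two lists with blocks of up to 6 could leave total arm sizes as much as 3 + 3 = 6 apart. Strata would be small: at an assumed 30% share about 15 children are breastfed, 7-8 per arm. Results within strata should therefore be descriptive, with the test resting on the combined estimate.
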